## 6. Criteria for Inclusion of Subjects:

Inclusion
Men or women (non pregnant) 18 years old or above
Diagnosed for Diabetes Mellitus (type 2)* and ADA criteria Diabetes (World-Health-Organization)
Evidence of peripheral neuropathy on neurologic examination Identified by our clinical staff examination and based on the criteria explained in ADA statement (Boulton et al, 2005)
Agreed to participate in this study and comply with instruction

May have a toe amputation

## 7. Criteria for Exclusion of Subjects:

Exclusion
Amputation and active ulcers or infection
Cognitive deficits. MMSE score of 24 or lower
Unable to stand for more than 5 minutes (including symptomatic orthostatic hypotension or pain)
Any clinically significant orthopedic, muscular, or peripheral vascular disorders that affect
Alcohol or substance abuse within 6 months or major psychiatric disorder.
Significant vision problem Less than 20/100 vision after correction
Any other neurological or medical disorders that may significantly affect balance based on clinical judgment (e.g. CVA, asymmetric)
Refusing or lacking medical decisional capacity to provide informed consent.
Use of medications that is likely to affect cognition or balance (based on physician review) within 14 days

## 8. Sources of Research Material:

Demographic information (age, gender, ethnicity), medical and social history, results of examinations of the feet, balance testing, responses to questionnaires, use of the electrical stimulation device, adverse events and treatment.

## 9. Recruitment Methods and Consenting Process:

Subjects will be recruited from the investigator's patient population at the Parkland ASC Clinic and the UTSW Wound Clinic. The Lead Coordinator or another member of the research team will identify potential subjects during a standard care visit and asked if they are interested in participation in this research. Subjects who express interest will be given a copy of the Consent to take home, read and discuss with family/friends. The Lead Coordinator will schedule a Screening Visit.

Subjects will be given ample time to read and consider the Consent and allowed to bring a family member or friend to the screening visit. Alternatives to participation will be presented and discussed.

The subject will also be told that a decision not to participate in the research will not affect his/her treatment relationship with the physician/investigator.

A member of the research team will review the Consent with the subject and answer any questions. If the subject agrees to participate, he/she will sign the Consent and HIPAA Authorization. He/She will receive copies of the signed documents. The consent process will be documented in the source file.

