**Figure 11**

**SENSUS™ Pain Management System**

Since most patients that participate in this project will have moderate to severe peripheral

sensory neuropathy, they will not be able to “feel” if they are receiving electrical stimulation. Placebo controls will have an electrical stimulation unit programmed not to provide any electrical current. However, all the other lights and programming indicators will be functional. Both active and inactive electrical stimulation units will be programmed to download the period that they are used on a weekly basis in order to verify that the units are used for the prescribed time period. A sealed randomization schedule envelope will be held at the coordinating center (UT Southwestern). Except in a medical emergency, subjects will remain blinded with regard to group assignment until crossover opportunity or such time that all source documentation is complete, e.g., transcription into the CRFs has been completed, CRFs have been signed by the Principal Investigator, and the database has been closed.

We will enroll a cohort of 80 diabetes (type II) patients with peripheral neuropathy (see section 6 for sample size justification). The diagnosis of diabetes mellitus will be based on World Health Organization criteria.(World-Health-Organization 1999). The inclusion and exclusion criteria are described in table III. The clinical assessments are described in table IV. The investigator will discuss the study design, duration, and its risks with potential subjects asked to participate. We will then provide the participant with a consent form to read at their leisure. The investigator will be available to answer questions or provide more explanation as requested by potential participants and their family.

Subjects will be recruited from two clinical centers: 1) Wound and Diabetic Foot center at the Hamad Medical Corporation (HMC-Doha-Qatar) under supervision of [name] (contact-LPI) and 2) the University of Texas Southwestern Medical Center (UT Southwestern), Dallas, Texas under supervision of [name] (Lead-PI).

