## **12. Procedures to Maintain Confidentiality:**

All study procedures will be conducted in the private treatment areas at UT Southwestern.

For participants who are screened but not eligible for participation in the study, their essential documents will be securely maintained and placed in a locked cabinet with all of the hard copies of the essential documents obtained during this research. For participants who are screened and then enrolled in the study, their essential documents will be filed with the individual's research file. The HIPAA Authorization covers all PHI collected through the course of the participation in the study in addition to that which is covered through the screening process.

Hard copy documents (source files) will be kept in locked cabinets in the locked research office. Electronic data will be stored on a dedicated research drive that is password-protected with access limited to members of the research team. No identified data will leave the campus. Presentations, papers and publications from this research will use only aggregate data and no personally identifiable information.

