To determine whether gait, balance, and physical activity variables change significantly across different study visit epochs, within-subject analyses of variance (ANOVA's) will be employed. We assume that plantar electrical stimulation is helpful to improve subjects gait, balance, and physical activity. Then sensor-derived movement variables should change substantially from baseline to the end of the study for the active group with no significant change in placebo group. For example, the range of motion of COM and RCI values should be reduced and gait velocity should be increased. Next, for all continuous variables, pretreatment scores will be regressed on post-treatment scores to form residualized change scores (e.g. VPT, monofilament test, pain intensity, A1C, etc). Correlations will then be generated among these scores to determine whether changes in sensor-derived movement factors are related appropriately with increases in (clinically assessed) functional capacities and self-report measures of activities, mood, socializing, etc. ANOVA test will be used to examine significant difference between intervention and sham group at baseline for age and BMI as well as the indicated outcomes (e.g. gait, balance, VPT, ABI,. Etc). We assumed there is no significant difference between sham and intervention group at baseline for the indicated variables. The same test will be repeated for the week 12. We assumed that the outcomes of study will be improved in the intervention group compared to the sham group. Paired- sample t-test will be used to examine the retention of the electrical stimulation therapy at two weeks post stopping the therapy compared to week-12. We assumed the benefit of the electrical stimulation therapy will be retained at least for two weeks. Additional analyses will examine the degree to which early-treatment changes in cognitive variables and functional capacity variables (representing functional restoration processes) predict late-treatment changes in moving ability post plantar electrical stimulation therapy. Such analyses will also allows to elucidate the relative contributions fear of falling (assessed using FES score); and/or and range of motion (assessed using body worn sensors) made to bringing about clinically meaningful changes in gait balance control. Moderator effects will also be examined for exploratory purposes. Using gender as an example, mixed design ANOVA's will be conducted to determine whether gait and balance factors change over the course of treatment at different rates or with different patterns for men and women as well as for patients with high or low severity of neuropathy and peripheral vascular disease. We assume those who have higher peripheral vascular problem will receive maximum benefit from electrical stimulation. Additional analyses will test whether changes in gait and balance variables predict changes in clinically important outcome factors (e.g., fear of falling (FES) , quality of life (SF12), adverse events, foot ulcer, etc) depending on gender.

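### The plan contradicts itself on whether Doha takes part, does not state site-stratified allocation, and compares the arms without site or baseline value, at a modest cost in precision

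*Combined protocol and SAP*

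**What the plan says.** **Sites.** Section 3 (Concise Summary of Project) states: "Subjects will be recruited from two clinical centers: 1) Wound and Diabetic Foot center at the Hamad Medical Corporation (HMC-Doha-Qatar", and then "2) the University of Texas Southwestern Medical Center (UT Southwestern), Dallas, Texas". Section 9 describes recruitment differently: "Subjects will be recruited from the investigator's patient population at the Parkland ASC Clinic and the UTSW Wound Clinic". Section 12 adds: "All study procedures will be conducted in the private treatment areas at UT Southwestern". Neither Section 9 nor Section 12 mentions Doha.

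**Allocation.** The only detail on the schedule is in Section 3: "A sealed randomization schedule envelope will be held at the coordinating center (UT Southwestern" is where it is kept. How the sequence is generated, whether it is blocked and whether there is a list per site are not stated. Section 3 also says that the study physicians are not blinded.

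**Analysis.** In Section 14 (Analysis Plan), "ANOVA test will be used to examine significant difference between intervention and sham group at baseline for age and BMI" and for the study outcomes, and the same test is then repeated at week 12. Between-group differences are also to be explored every two weeks during treatment. No site term appears. Pre-treatment values enter only through residualized change scores, which feed correlations and not the arm comparison. The moderators listed are gender, neuropathy severity and peripheral vascular disease; site is not among them.

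**The concern.** If Section 3 is right, recruitment and procedures for one of two centres are undescribed. If Sections 9 and 12 are right, the two-centre statement is wrong. A reader cannot tell how many sites the analysis has to handle.

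If there are two sites, in different countries, outcome levels may differ between them. The plan itself expects response to vary with vascular disease, so patient mix could matter. When allocation is not balanced by site and the model ignores site, the arms can differ in site mix by chance, and the between-arm comparison carries that extra variation. The baseline value, which the trial collects for the balance, gait, neuropathy and perfusion outcomes, is also left out of this comparison. What is at stake is avoidable loss of precision in the main comparison of arms.

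**Working it through.** **1. The plan's own figure.** Section 14 gives improvement rates of 50% and 10%, 85% power, two-sided 5%, and 27 per group. With mean rate 0.30:

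- Uncorrected n = [1.960·√(2·0.3·0.7) + 1.036·√(0.25 + 0.09)]² / 0.4² = (1.270 + 0.604)² / 0.16 ≈ 22.
- Continuity-corrected n = (21.96/4)·[1 + √(1 + 4/(21.96·0.4))]² ≈ 26.7, so 27.

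The stated 27 reproduces. The calculation makes no allowance for site.

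**2. Inputs for the site check.** From Section 14: 40 per arm enrolled, 10% dropout, so 40 × 0.9 = 36 evaluable per arm. Assumed, because the documents give neither: site split p = 50:50 (70:30 as an alternative), and a between-site gap g of 0.25 to 1.0 within-site SD.

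**3. Chance imbalance if allocation is not stratified.** With 80 patients, 40 per arm and 40 per site, the number of one site's patients in the active arm is hypergeometric. The SD of the difference in site share is 0.1125.

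- 50:50 split: the probability of a difference of at least 10 points is 0.50, and of at least 20 points 0.117.
- 70:30 split: 0.46 and 0.087.

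A 20-point imbalance shifts the unadjusted difference by 0.2g, that is 0.05 to 0.20 SD over the assumed range.

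**4. Imbalance and noise are one effect.** Take g = 0.5 and 40 per arm. The SD of the shift is 0.5 × 0.5·√(2/40) = 0.056. The standard error of the arm difference is √(2/40) = 0.224. Then (0.056/0.224)² = 0.0625. The usual variance inflation is p(1−p)g² = 0.25 × 0.25 = 0.0625, the same quantity. It must be counted once.

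**5. Cost in power.** The standardized effect that gives 85% power at 27 per group is (1.960 + 1.036)·√(2/27) = 0.8155. Variance is multiplied by 1 + 0.25g², and power = Φ(0.8155/√(2(1 + 0.25g²)/n) − 1.960).

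| Gap g (SD) | Variance increase | Equivalent of 27 per group | Power, 27 per arm | Power, 36 per arm |
|---|---|---|---|---|
| 0 | 0 | 27 | 85.0% | 93.3% |
| 0.25 | 1.6% | 28 | 84.5% | 93.0% |
| 0.5 | 6.3% | 29 | 82.8% | 91.9% |
| 0.8 | 16% | 32 | 79.4% | 89.5% |
| 1.0 | 25% | 34 | 76.4% | 87.2% |

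If the 27 per group already contains site variation, the same step read the other way says that a site term would raise power at 36 per arm from 93.3% to between 93.7% and 97.2%.

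**The case against.** The strongest reply is that the effect is small and its size assumed. At 36 per arm, a gap of 0.5 SD costs 1.4 points of power; it takes a full 1.0 SD to cost 6.1. Nothing in the documents shows that the sites differ at all, and the same named devices and test procedures apply throughout. That stands. It limits the size of the point, not the point itself.

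Four stronger readings are tempting, and the documents do not support them.

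- *Allocation is not stratified by site.* Section 3 says only where the schedule is held. A stratified schedule could be stored in the same way. Stratification is unstated, not shown to be absent.
- *Leaving out site biases the result, on top of adding noise.* Step 4 shows these to be one effect, already reflected in the unadjusted error term. Randomization keeps the test valid and the estimate unbiased on average.
- *Every planned comparison is affected.* Within-subject ANOVAs and paired t-tests cancel stable site levels. The gain falls mainly on the between-arm comparisons.
- *The loss equals a fixed number of patients.* Taking site to explain 20% of variance, or 16 of 80 patients, uses the 1.0 SD end of an assumed range. An equal split of 40 per site is likewise an assumption.

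Two further points are fair. The sample-size text speaks of comparing changes, which would remove stable site levels, but the Analysis Plan does not carry that into the week-12 test. The Dallas-only wording may be local text for one site; even so, it contradicts Section 3 as written.

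**Conclusion.** The point holds as a contradiction to resolve and an inexpensive gain forgone, not as a threat to validity. The conflict between Section 3 and Sections 9 and 12 needs no assumption. If there are two sites, the stated between-arm ANOVA gives up precision that site and baseline adjustment could recover.

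The loss is about 0.3 to 6.1 power points at 36 per arm. It rests on the assumed 50:50 split, the assumed gaps, no stratification, and 27 per group giving 85% power. Site's own contribution would be smaller once baseline is in the model, because the baseline value absorbs part of any stable site difference.

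The power reserve at 36 per arm also depends on that basis. The pilot sway figures in Section 14 (week-2 difference 4.94 − 3.49 = 1.45, pooled SD √((1.25² + 3.42²)/2) = 2.575) give only 54% power at 27 per group and 71% at 40. On the balance outcome there is no surplus to absorb a loss.

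**What to change.** 1. Reconcile Sections 3, 9 and 12: state which centres recruit, and where consent and assessments take place.
2. In Section 14, replace the between-arm ANOVA at the end of treatment and at the earlier treatment visits with an ANCOVA of the outcome on arm, baseline value and site (fixed effect), specified before unblinding. This can be done even if recruitment is under way. Section 14 dates the last treatment visit at week 12, while Section 4 schedules treatment visits only to week 6; that difference must be reconciled separately so that the model has a defined time point.
3. State whether allocation is stratified by site. If recruitment has not started, use a separate list per site with varying, concealed block sizes. The concealment matters because the study physicians are unblinded, and small or fixed blocks would make later allocations easier to predict.

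Cost: one degree of freedom for site and one for baseline. With 72 evaluable patients (2 × 36), residual degrees of freedom go from 70 to 68. No new data are needed for outcomes already measured at baseline. Separate lists add a little work in preparing the schedule.

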## **10. Potential Risks:**

### *Study Intervention*

In previous clinical research, no risks have been identified with the SENSU (Neurometrix, Inc. ; <http://www.sensusrx.com/> ) That is, no previous subjects have experienced any adverse events (side effects) from wearing the device.

### *Loss of Confidentiality*

Any time information is collected; there is a potential risk of loss of confidentiality.

### *Other Risks*

There may possibly be other side effects that are unknown at this time.

## **11. Subject Safety and Data Monitoring:**

The principal investigator will monitor the experience of the subjects at least monthly and the conduct of the protocol, including:

- Study accrual rate
- Experience of study participants
- Study attrition including participant withdrawals/dropouts
- Patterns of AEs and/or unanticipated events
- Patterns of protocol deviations and/or violations
- Changes in risk/benefit

## **12. Procedures to Maintain Confidentiality:**

All study procedures will be conducted in the private treatment areas at UT Southwestern.

For participants who are screened but not eligible for participation in the study, their essential documents will be securely maintained and placed in a locked cabinet with all of the hard copies of the essential documents obtained during this research. For participants who are screened and then enrolled in the study, their essential documents will be filed with the individual's research file. The HIPAA Authorization covers all PHI collected through the course of the participation in the study in addition to that which is covered through the screening process.

Hard copy documents (source files) will be kept in locked cabinets in the locked research office. Electronic data will be stored on a dedicated research drive that is password-protected with access limited to members of the research team. No identified data will leave the campus. Presentations, papers and publications from this research will use only aggregate data and no personally identifiable information.

### **13. Potential Benefits:**

Wearing the Sensus stimulator may improve balance, circulation (blood flow), and quality of life, but this cannot be guaranteed.

We hope the information learned from this study will benefit others with diabetic peripheral neuropathy in the future. Information gained from this research could lead to better treatment.

### **14. Biostatistics:**

**Power & Sample Size Estimation:** The sample size for the study was designed to achieve 85% power when comparing the change in the actively treated group to the change in the sham treated group, using assumed rates of 50% and 10% improvement, respectively. A two-sided test of results in evaluable subjects (qualified for analyses of efficacy on vibration perception threshold and on structured S-W monofilament testing) will provide the specified power at a 5% significance level. Sample size calculations resulted in a requirement for a total of twenty-seven (27) subjects in each group. The sample size was also estimated using our pilot data in which we explored the benefit of plantar stimulation for improving balance (Study 5). At baseline, the area of sway for center of mass (COM) was  $5.23 \pm 2.81 \text{ cm}^2$  and  $5.41 \pm 1.14 \text{ cm}^2$  respectively for the sham and intervention groups. After week two of treatment, the area of COM sway was  $4.94 \pm 3.42 \text{ cm}^2$  for the sham and  $3.49 \pm 1.25 \text{ cm}^2$  for the intervention group. Using the same criteria explained above, to observe a significant improvement in the intervention group receiving active stimulation compared to sham group (with nonfunctional stimulator), twenty seven subjects per group is required. Assuming 10% drop out, therefore, 40 subjects per group (a total of 80 subjects) should be enough for the purpose of this study.

No suitable alternative treatments exist for patients with loss of protective sensation due to diabetic peripheral neuropathy, so a statistically detected difference in improvement between groups may be considered a clinically meaningful result. However, the study was designed to detect a sufficiently large difference to account for an anticipated “placebo effect” in the sham treated group.

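### The 85% power claim is for a comparison of change, but the only between-arm outcome test named is an ANOVA of week-12 values, which has about 65–75% power for COM sway at 36 evaluable per group on the pilot figures

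*Combined protocol and SAP*

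**What the plan says.** The Power & Sample Size paragraph of Section 14 states that the trial was "designed to achieve 85% power when comparing the change in the actively treated group to the change in the sham treated group", with assumed improvement rates of 50% and 10%. It describes "A two-sided test of results in evaluable subjects (qualified for analyses of efficacy on vibration perception threshold and on structured S-W monofilament testing") at the 5% level and arrives at 27 per group.

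A second calculation, under the same criteria, uses COM sway area from the pilot trial (Study 5 in Section 2). Baseline means and SDs are 5.23 ± 2.81 cm² (sham) and 5.41 ± 1.14 cm² (active). For the follow-up values, "After week two of treatment, the area of COM sway was" 4.94 ± 3.42 cm² (sham) and 3.49 ± 1.25 cm² (active). The paragraph again concludes that "twenty seven subjects per group is required. Assuming 10% drop out, therefore, 40 subjects per group (a total of 80 subjects) should be enough".

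The Analysis Plan says "ANOVA test will be used to examine significant difference between intervention and sham group at baseline", for age, BMI and the outcomes, and then "The same test will be repeated for the week 12". It also says that "pretreatment scores will be regressed on post-treatment scores to form residualized change scores", but the next step is that "Correlations will then be generated among these scores". It mentions primary and secondary endpoints without saying which outcome is primary, and it names no test for the two-weekly between-group comparisons.

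**The concern.** The power statement concerns a difference in change between arms. The named arm test compares values at one visit. These two analyses have different variances, so a sample size for one does not carry over to the other. The change comparison depends on the correlation r between baseline and follow-up, which is not stated.

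Nothing else in the Analysis Plan fills the gap. The within-subject ANOVAs run across visits with no arm factor stated. The residualized change scores are used for correlations. The mixed-design ANOVAs are exploratory and examine gender and disease severity. The improvement rates in the first calculation have no matching test of proportions in the Analysis Plan.

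If the named test is used, a balance effect of pilot size could be missed more often than the plan implies, and a null result on hypothesis H1 could be read as no effect. With no designated primary outcome, over 30 gait parameters alone and a flat 0.05 threshold, a positive result could also be picked from many. Section 1 intends to plan a later randomized trial from these data, so either error would carry forward.

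**Working it through.** **Inputs.** All are from Section 14 unless noted: two-sided α = 0.05 and power 85% (z sum 1.960 + 1.036 = 2.996); the sway means and SDs above; 40 enrolled per group; 10% drop-out. Section 2 (Study 5) says balance was measured in 13 subjects. The correlation r is not in the documents and is varied as an assumption.

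**1. The plan's first figure, 50% against 10%.** Mean proportion 0.30.
- n = [1.960·√(2·0.30·0.70) + 1.036·√(0.25 + 0.09)]² / 0.40² = 22.0
- With continuity correction: (22.0/4)·[1 + √(1 + 4/(22.0·0.40))]² = 26.7, so 27. The stated figure reproduces.

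**2. Effects available from the pilot.**
- Difference in week-2 values: 4.94 − 3.49 = 1.45
- Difference in change: (5.41 − 3.49) − (5.23 − 4.94) = 1.63

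The gap of 0.18 is the pilot's baseline imbalance. If the arms are equal at baseline, as the Specific Aim 1 text and the Analysis Plan assume, 1.63 can also be taken as the expected difference in follow-up values.

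**3. ANOVA of follow-up values (the named test).** Pooled SD = √[(3.42² + 1.25²)/2] = 2.575, and n = 2·2.575²·2.996²/effect².
- Effect 1.45: 56.6, so 57 per group (58 by noncentral t)
- Effect 1.63: 44.8, so 45 per group (46 by noncentral t)

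Power by noncentral t:

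| n per group | effect 1.45 | effect 1.63 |
|---|---|---|
| 27 | 53% | 63% |
| 36 | 65% | 75% |
| 40 | 70% | 80% |

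**4. Comparison of change.** The two group variances are 2.81² + 3.42² − 2r(2.81)(3.42) and 1.14² + 1.25² − 2r(1.14)(1.25). Their sum is 22.45 − 22.07r, and n = (22.45 − 22.07r)·2.996²/effect². Setting n = 27 gives r = 0.66 (effect 1.63) or 0.73 (effect 1.45); by noncentral t, 0.67 or 0.74. At 36 per group, 85% needs r of about 0.55 (1.63) or 0.65 (1.45).

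**5. Baseline-adjusted comparison (ANCOVA).** SD = 2.575·√(1 − r²), 69 degrees of freedom. It reaches 85% at 36 per group with r of about 0.47 (1.63) or 0.62 (1.45).

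Power at 36 per group, shown as effect 1.45 / effect 1.63:

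| r | change scores | ANCOVA |
|---|---|---|
| 0 | 44% / 53% | 65% / 75% |
| 0.3 | 58% / 68% | 70% / 79% |
| 0.5 | 72% / 81% | 78% / 86% |
| 0.6 | 81% / 89% | 84% / 91% |

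A simulation of the ANCOVA with the unequal arm SDs (4,000 runs) agrees within about 1.5 percentage points: 68/78%, 78/86% and 84/90% at r = 0.3, 0.5 and 0.6.

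**6. Pilot precision.** The arm split of the 13 subjects is not given. The standard error of the week-2 difference is √[3.42²/a + 1.25²/(13 − a)] with a sham subjects. It is 1.76 at a = 4 and 1.30 at a = 9, about as large as the effect itself.

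**7. Drop-out.** 27/0.9 = 30, not 40. Enrolling 40 leaves 40 × 0.9 = 36; going from 40 to 27 would be a 32.5% loss.

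**The case against.** The quoted 85% introduces the 50% against 10% calculation, and that reproduces. The sway-based 27 can also be right as a change comparison: the team held the pilot data, could have computed the SD of change directly, and may only have left it out of the text. The trial enrols 40 per group, not 27. At r = 0.655 a change comparison with 36 per group has about 86% power (effect 1.45) or 93% (effect 1.63). On this view the Analysis Plan is loosely written and the intended test may well be one of change. Further, every sway figure rests on 13 subjects at week 2, and the Specific Aim 1 text quantifies postural control by COM range of motion, whereas the pilot figures are sway area.

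Much of this stands as a limit on the numbers. No error is shown in the first calculation, the second cannot be called wrong for a change analysis, and the over-enrolment narrows the gap. It does not remove the point. The 85% criterion is carried explicitly to sway, the one arm test that is named is not a change analysis, and it stays below 85% even with all 40 per group. If a change analysis was meant, the plan must name it and state r, because at r = 0.3 it would have only 58–68% power at 36 per group. The weakness of the pilot argues for a range in place of a single 85%. The two-sided test mentioned for vibration perception and monofilament results is not identified anywhere in the Analysis Plan.

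**Conclusion.** The concern holds and should be fixed. The analysis that is powered is not the analysis that is named, and neither sample-size calculation is tied to a designated primary outcome and its test. If the week-12 ANOVA is used, power for a pilot-sized sway effect is about 65–75% at 36 evaluable per group, so the effect would be missed about 25–35% of the time rather than the 15% implied. These are scenarios, not a measured shortfall: they take week-2 sway area from 13 subjects as a guide to week 12, pool very unequal SDs, and use effects of 1.45 to 1.63 cm². Confidence in the mismatch is high; confidence in the exact size of the power loss is low. The drop-out arithmetic is a minor slip in the safe direction.

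**What to change.** Keep 80 patients and revise Section 14:

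1. Replace the raw week-12 ANOVA with a baseline-adjusted comparison between arms (ANCOVA) for the continuous outcomes, using the baseline values already collected.
2. Restate COM sway power at 36 per group for that test as a range over the two effects and over r (70–79% at r = 0.3, 78–86% at 0.5, 84–91% at 0.6), and say that the inputs are sway area from 13 pilot subjects at week 2.
3. Correct the drop-out line: 30 needed after allowing for 10% loss, 40 enrolled, 36 expected evaluable.
4. Have the sponsor designate one primary outcome, with its measure, test condition and time point, before any outcome data are examined by arm. Doing so before unblinding is not a sufficient safeguard, because Section 3 leaves the study physicians unblinded. COM sway would fit Aim 1, but the choice is the sponsor's. Label the other outcomes secondary or exploratory and tie the power statement to the primary outcome. If that is a vibration or monofilament responder outcome, add the matching test of two proportions.
5. Reconcile the last on-treatment visit, which is week 6 in Section 4 and Table IV but week 12 in Section 1 and the Analysis Plan. As written, the week-12 test has no scheduled visit.

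The cost is wording in Section 14 plus the visit reconciliation, with no extra patients, visits or measurements. ANCOVA uses one degree of freedom, and even at r = 0 its power stays at about 65–75%. The drawback is that the stated power looks less favourable unless r is high, and the non-primary outcomes lose confirmatory status.
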